This stage is designed to determine if daily oral ACZ is tolerated and if tachyphylaxis might occur with long-term use for the specific formulation of oral ACZ that we will utilize. Some authors have reported attenuation of the initial increases in CBF with sustained use or oral ACZ though still showing a persistent increase in cerebral perfusion of between 15% - 20%, when compared to pre-treatment levels (Friberg et al., 1990). In this stage, all subjects will receive baseline pCASL and DSC MRI and will start oral ACZ. Patients will continue on 1000 mg BID dose for 24 consecutive weeks and undergo repeat imaging at predetermined intervals. MRI scans and clinical evaluations will be obtained every 6 weeks with contrast-based scans repeated every 12 weeks. Contrast will be administered every 12 weeks to determine DSC measures of blood flow and whether new lesions have formed. As previously stated, DSC provides measurements of not only CBF but also blood volume (CBV) and transit time of blood (MTT). DSC techniques will provide information that cannot be obtained by using pCASL alone that might be important to determine how blood flow is altered with ACZ.

Stage 3 - Many factors contribute to the formation and evolution of lesions in MS (Cotton et al., 2003; Meier and Guttmann, 2006; Narayana et al., 1998). As much as 60% of MS lesions resolve over six

months while the remainder show evidence of persistent damage (Sahraian et al., 2010). In this stage, all subjects will receive baseline pCASL and DSC MRI and will then be randomized to first receive either daily oral therapy with either "**Treatment A**", extended-release ACZ capsules or "**Treatment B**", placebo capsules for 24 consecutive weeks and undergo repeat imaging at predetermined intervals. MRI scans and clinical evaluations will be obtained every 6 weeks with contrast-based scans repeated every 12 weeks. Contrast will be administered every 12 weeks to determine DSC measures of blood flow and whether new lesions have formed and determine how blood flow is altered with ACZ.

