At the end of week 24, patients initially randomized to Treatment B will take 1000 mg extendedrelease ACZ capsules. Similar imaging and clinical evaluations will be performed for the second 24week period. All subjects will discontinue drug at week 48 and obtain a follow-up clinical visit two weeks later. Based upon established pharmacokinetics, the half-life of drug is between 60-75 hours and one would expect insignificant levels within two weeks of discontinuation.

To maintain blinding, patients, evaluating clinicians and MRI analysts will not be informed of treatment assignment or sequence of scans.

We anticipate that sustained increases in regional cerebral perfusion over 6 months will result in improved tissue integrity as measured using diffusion tensor metrics and fewer MS lesions that evolve to persistent black holes.

HYPOTHESIS AND OBJECTIVES

Hypothesis

The underlying hypothesis of this proposal is that long-term therapy with ACZ will improve cerebral perfusion in subjects with MS and this improved perfusion will result in improved tissue integrity in a proportion of MS lesions. To test this hypothesis, subjects will be treated with ACZ, a currently FDA approved agent previously shown in healthy controls to increase cerebral perfusion (Sullivan et al., 1987; Vagal et al., 2009). Subjects will be scanned at various time points (see sections 4 and 6.3) and quantitative MRI metrics will be used to evaluate lesion evolution during and after discontinuation

of treatment.

Primary & Key Secondary Objective

Determine the degree to which divided daily doses of ACZ improves global and regional cerebral perfusion in subjects with MS.

Study subjects will obtain serial MRI scans prior to, during and after therapy (see sections 4 and 6.3). Cerebral blood flow will be measured using an optimized pCASL technique as described by Aslan (Aslan et al., 2010). This will allow us to test the first component of our hypothesis that treatment with ACZ will result in increased regional and/or global perfusion.

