	Day -7 Screen	Wk 0 Visit 1	Wk 2 Visit 2	Wk 4 Visit 3	Wk 6 Visit 4	Wk 8 Visit 6					
Treatment		500 mg PO BID	1000 mg PO BID	1500 mg PO BID	2000 mg PO BID						
H&P	Х	Х	Х	Х	Х	Х					
CBC, CMP	Х					Х					
Urine pregnancy*	Х										
pCASL MRI		Х	Х	Х	Х	Х					
MSFC		Х	Х	Х	Х	Х					
EDSS		Х	Х	Х	Х	Х					
Blood Sample X X X X X X											
* Female participants who have already been evaluated for pregnancy will not be retested unless otherwise indicated											

•												

Stage 2a – Safety/Tolerability & Kinetics of Treatment Effect										
Up to a Total of 10 subjects										
	Wk -4 Screen	Wk 0 Visit 1	Wk 6 Visit 2	Wk 12 Visit 3	Wk 14 Visit 4					
Treatment		1000 mg ACZ BID		d/c ACZ						
H&P	Х	X	Х	Х	Х					
CBC, CMP		X	Х	Х	Х					
Urine pregnancy*		X								
DSC MRI		X		Х						
pCASL MRI		X	X	x	X					
MSFC		X	Х	Х	Х					
EDSS		X	Х	Х	Х					
MFIS, MSWS-12		X	X	x	X					
Blood Sample		X	X	X	X					
* Female pa unless other	rticipants who wise indicated	have already been evaluated	for pregnancy	/ will not be r	retested					

- Additional CBC,CMP will be performed if measured ALT/AST > 1X ULN or if other alterations above baseline

- EDSS Expanded disability status scale
- MSFC Multiple Sclerosis Functional Composite Scale

Stage 2b – Tolerability & Tachyphylaxis of ACZ in MS Subjects									
• Up	to a Tota	I of 10 subjects		-					
	Wk -1 Screen	Wk 0 Visit 1	Wk 6 Visit 2	Wk 12 Visit 3	Wk 18 Visit 4	Wk 24 Visit 5			
Treatment		ACZ at dose identified in Stage 1b							
H&P	Х	X	X	Х	Х	Х			
CBC, CMP		Х	Х	Х	Х	Х			
Urine		Х							
pregnancy*									
DSC MRI		Х		Х		Х			
pCASL MRI		X	Х	X	x	Х			
MSFC		Х	Х	Х	Х	Х			
EDSS		Х	Х	Х	Х	Х			
MFIS, MSWS-12		X	Х	Х	х	Х			
Blood Sample		X	Х	Х	X	X			
* Female pa otherwise in	rticipants v dicated	who have already been evaluat	ed for pregna	ncy will not b	be retested u	nless			

- Additional CBC,CMP will be performed if measured ALT/AST > 1X ULN or if other alterations above baseline
- EDSS Expanded disability status scale
- MSFC Multiple Sclerosis Functional Composite Scale

Stage 3 – F	RCT; Lor	ng-term ther	apy wit	h ACZ	in MS S	Subject	S				
Del	layed-sta	rt design with	n oral th	erapy "	'Treatm	ent A"	(ACZ) o	or "Trea	tment l	B" (placebo)
 Tot 	al of 60 s	subjects									
	Wk -1 Screen	Wk 0 Visit 1	Wk 6 Visit 2	Wk 12 Visit 3	Wk 18 Visit 4	Wk 24 Visit 5	Wk 30 Visit 7	Wk 36 Visit 8	Wk 42 Visit 9	Wk 48 Visit 10	Wk 50 Visit 11
Treatment		Randomize to ACZ or placebo								d/c treatment	End Study
H&P	Х	Х	Х	Х	Х	Х	Х	Х	Х	Х	

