Visit 1 – Subjects will be randomized to receive Treatment A or Treatment B first for the initial 24 weeks. Subjects will receive MRI brain with and without gadolinium contrast utilizing MRI sequences as detailed in Stage 2a.

Subjects will be contacted by telephone or email monthly to document tolerability and encouraged to report any AE occurring with drug at any point during the study.

Visit 2 – Subjects will receive a complete medical and neurological examination, MSFC & EDSS evaluation as well as patient-reported clinical disability measures (MFIS & MSWS-12) and will be asked questions to ascertain tolerability to daily therapy. All subjects will obtain MRI brain without gadolinium contrast utilizing the sequences described above except for DSC sequence.

Visit 3 – Subjects will receive a complete medical and neurological examination, MSFC & EDSS evaluation as well as patient-reported clinical disability measures (MFIS & MSWS-12) and will be asked questions to ascertain tolerability to daily therapy. All subjects will obtain MRI brain with and without gadolinium contrast utilizing the sequences described above.

Visit 4 – Subjects will receive a complete medical and neurological examination, MSFC & EDSS evaluation as well as patient-reported clinical disability measures (MFIS & MSWS-12) and will be asked questions to ascertain tolerability to daily therapy. All subjects will obtain MRI brain

without gadolinium contrast utilizing the sequences described above except for DSC sequence.

Visit 5 – Subjects will receive a complete medical and neurological examination, MSFC & EDSS evaluation as well as patient-reported clinical disability measures (MFIS & MSWS-12) and will be asked questions to ascertain tolerability to daily therapy. All subjects will obtain MRI brain with and without gadolinium contrast utilizing the sequences described above.

Upon completion of the MRI scan, subjects previously treated with Treatment B will start Treatment A and all subjects will continue on Treatment A for the remaining 24 weeks of the study.

Visit 6 – Subjects will receive a complete medical and neurological examination, MSFC & EDSS evaluation as well as patient-reported clinical disability measures (MFIS & MSWS-12) and will be asked questions to ascertain tolerability to daily therapy. All subjects will obtain MRI brain with and without gadolinium contrast utilizing the sequences described above.

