Visit 7 – Subjects will receive a complete medical and neurological examination, MSFC & EDSS evaluation as well as patient-reported clinical disability measures (MFIS & MSWS-12) and will be asked questions to ascertain tolerability to daily therapy. All subjects will obtain MRI brain without gadolinium contrast utilizing the sequences described above except for DSC sequence.

Visit 8 – Subjects will receive a complete medical and neurological examination, MSFC & EDSS evaluation as well as patient-reported clinical disability measures (MFIS & MSWS-12) and will be asked questions to ascertain tolerability to daily therapy. All subjects will obtain MRI brain with and without gadolinium contrast utilizing the sequences described above.

Visit 9 – Subjects will receive a complete medical and neurological examination, MSFC & EDSS evaluation as well as patient-reported clinical disability measures (MFIS & MSWS-12) and will be asked questions to ascertain tolerability to daily therapy. All subjects will obtain MRI brain without gadolinium contrast utilizing the sequences described above except for DSC sequence.

Visit 10 – Subjects will receive a complete medical and neurological examination, MSFC & EDSS evaluation as well as patient-reported clinical disability measures (MFIS & MSWS-12) and will be asked questions to ascertain tolerability to daily therapy. All subjects will obtain MRI brain with and without gadolinium contrast utilizing the sequences described above. Upon completion of the brain MRI, all subjects will be instructed to discontinue assigned treatment.

Visit 11 – Subjects will receive a complete medical and neurological examination, MSFC & EDSS evaluation as well as patient-reported clinical disability measures (MFIS & MSWS-12) and will be asked questions to ascertain any other AEs after discontinuation of therapy. All subjects will obtain MRI brain without gadolinium contrast utilizing the sequences described above except for DSC sequence.

Subjects will be contacted by telephone or email monthly to document tolerability and encouraged to report any AE occurring with drug at any point during the study.

For any part of the study, a subject whose CBC or CMP is not at or near baseline values will repeat these blood tests.

a. Final Study Visit:

The final study visit will be used to document any potential adverse event associated with treatment arm, not previously documented.

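### Stage 3 visit text includes a Visit 6 with gadolinium MRI that the schedule table lacks: six contrast scans per subject in the text, five in the table and under the 12-weekly rule

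*Combined protocol and SAP*

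**What the plan says.** Three places in the combined protocol and SAP set the Stage 3 imaging schedule.

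- **Design text** (Rationale for Study Design, Stage 3): "MRI scans and clinical evaluations will be obtained every 6 weeks with contrast-based scans repeated every 12 weeks". For weeks 24 to 48 it adds: "Similar imaging and clinical evaluations will be performed for the second 24week period".
- **Schedule table** (Trial Schedule, Stage 3): the header passes from week 24 to week 30 as "Wk 24 Visit 5 Wk 30 Visit 7", with no Visit 6 column. DSC MRI, the contrast-based scan, is marked at weeks 0, 12, 24, 36 and 48.
- **Visit text** (Study Visits and Procedures, Stage 3): Visits 1 to 11 are described with no gap in the numbering. At Visit 1, "Subjects will receive MRI brain with and without gadolinium contrast utilizing MRI sequences as detailed in Stage 2a". At Visits 3, 5, 6, 8 and 10 the same sentence appears: "All subjects will obtain MRI brain with and without gadolinium contrast utilizing the sequences described above". At Visits 2, 4, 7, 9 and 11 it is instead: "All subjects will obtain MRI brain without gadolinium contrast utilizing the sequences described above except for DSC sequence".

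Visit 5 is the week-24 switch: "Upon completion of the MRI scan, subjects previously treated with Treatment B will start Treatment A". The Visit 6 entry follows it and is complete in itself, with examination, MSFC, EDSS, MFIS, MSWS-12 and a gadolinium MRI.

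**The concern.** The visit text tells staff what to do at each attendance, and it contains a full attendance with a contrast injection that the table does not date. Taken in order, Visit 6 falls after the week-24 scan and before week 30, so two contrast administrations would lie within six weeks of each other where the design text spaces them at 12.

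What is at stake is mainly each subject's contrast exposure, which an operative protocol should state without ambiguity; the protocol itself describes risks of gadolinium in the Rationale for Study Design. Whichever passage a site follows, it departs from another. An extra visit would also yield CBF, CBV and MTT readings and an enhancing-lesion assessment at a time that the schedule does not define.

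**Working it through.** This is a count; no sample-size formula applies. The inputs are the Stage 3 table, the Stage 3 visit text and the 12-weekly contrast rule.

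**1. The table's figure, reproduced from the design rule.** Contrast every 12 weeks from week 0 to week 48 gives 48/12 + 1 = 5 scans, at weeks 0, 12, 24, 36 and 48. These are the five DSC marks in the table. (The document prints no total; five is counted.)

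**2. Visit text against table.**

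| Visit | Visit text | Week in table | DSC mark in table |
|---|---|---|---|
| 1 | with gadolinium | 0 | yes |
| 2 | without | 6 | no |
| 3 | with | 12 | yes |
| 4 | without | 18 | no |
| 5 (switch) | with | 24 | yes |
| **6** | **with** | **none** | **none** |
| 7 | without | 30 | no |
| 8 | with | 36 | yes |
| 9 | without | 42 | no |
| 10 | with | 48 | yes |
| 11 | without | 50 | no |

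**3. Totals per subject.**

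- Contrast scans: 6 in the text (Visits 1, 3, 5, 6, 8, 10); 5 in the table. Difference: 6 − 5 = 1.
- MRI visits: 11 in the text. The table marks pCASL at weeks 0 to 48 every 6 weeks (48/6 + 1 = 9) and at week 50, so 9 + 1 = 10. Difference: 11 − 10 = 1.
- With Visit 6 left out of the count, the text gives 5 contrast scans and 10 MRI visits, and agrees with the table at every visit.

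**4. Can Visit 6 be fitted to a week already in the table?**

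- Not week 24: Visit 5 is that scan, and the switch follows its completion.
- Not week 30: the table marks no DSC there, and Visits 7 to 11 would no longer match their weeks.
- No 6-weekly time point lies strictly between weeks 24 and 30.

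**5. Is a table column missing from the extracted text?** Probably not. The printed weeks run evenly from 0 to 48 in steps of 6, and the DSC marks alternate regularly across them.

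**6. Size across Stage 3.** The table plans 60 subjects: 60 × 1 = 60 administrations at most. With the 18% dropout in Sample Size and Statistical Methods, 60 × 0.82 = 49.2, close to the 50 on which the power calculation is based.

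**The case against.** The strongest reply is that Visit 6 would probably never be carried out. Apart from the 24-week markers at Visits 1 and 5, the visit text dates no attendance; a visit is booked from the table, and the table has no Visit 6. A query or a skipped visit is at least as likely as an injection. This stands: a reader might infer that following the visit text would lead to an extra injection, but the documents show only that the instructions conflict.

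The entry may also be a leftover. Visits 6 to 10 repeat the with/without pattern of Visits 1 to 5, as a second-period baseline would, and crossover wording survives in the Summary of Study Design and in the objectives. This is plausible, but the documents do not say so. A reader might go on to conclude that the table is right and the Visit 6 scan is unplanned; that does not follow from the text.

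On the analysis, the primary outcome is change in global CBF from baseline to week 24, before any Visit 6. The phase-2 comparison is change in global CBF from week 24 to week 48, and both of those scans are scheduled. CBF is measured by pCASL, so the contrast status of Visit 6 does not determine it. A reader might infer that the phase-2 model is compromised; no bias or loss of precision can be shown from the documents. What remains is that a Visit 6 reading, if taken, has no assigned time in models that include time and, for clinical outcomes, use CBF, CBV and MTT as time-varying covariates.

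On risk, the protocol regards the chance of an anaphylactic reaction as very low, links nephrogenic systemic fibrosis to moderate to severe renal disease and dialysis, excludes patients with renal disease, and provides for reactions at the imaging centre. This tempers the safety argument. It does not remove the need for one stated number of contrast administrations.

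**Conclusion.** The contradiction is real and follows from a direct count: six contrast scans and 11 MRI visits in the Stage 3 visit text, five contrast scans and 10 pCASL visits in the table, and five contrast scans under the 12-weekly rule. Visit 6 accounts for the whole difference.

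One contrast administration per subject is in dispute. The figure of 60 is a ceiling: it assumes that every randomised subject stays past week 24 and receives a scan that has no date. About 50 is the corresponding figure if the planned dropout has all occurred by then. Neither is a forecast of injections that will be given.

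The sample size and the week-24 primary analysis are unaffected, and the week 24-to-48 CBF comparison keeps both of its scheduled scans. This is an internal inconsistency in an operative clinical procedure. It should be corrected, but it does not threaten the main result. Which version is intended cannot be settled from the documents.

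**What to change.** Reconcile the Stage 3 entries in Study Visits and Procedures, the Stage 3 schedule table and the Stage 3 design text, so that all three agree on whether Visit 6 exists. If it does, state its week and its contrast status in the text and the table, make the stated scan intervals consistent with it, and say how its measurements enter the week 24-to-48 models. If it does not, remove the entry.

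Either way, keep Visits 7 to 11 numbered alike in text and table. They match now, so renumbering the text alone would create a new mismatch. The decision belongs to the sponsor and the investigator.

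The cost is protocol wording only; the sample size and the primary analysis do not change.
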